4.2.4 Analysis of the primary variable

Under a proportional hazard assumption, we can define the hazard ratio as $\theta = H_A(t)/H_B(t)$ for all $t \leq \tau$, τ is the largest observation time. A represents the active treatment arm (AZD1419), B represents placebo and $H(t)$ is the hazard function. To compare the effect of active treatment AZD1419 to placebo group, a log-rank (Mantel-Cox χ^2) test will be carried out using the SAS[®] procedure PROC LIFETEST, where the null hypotheses will be:

$$H_0: \theta = 1$$

$$H_1: \theta < 1$$

The null hypothesis (H_0) is that during the 52-week double-blind treatment period, the time to loss of asthma control in the AZD1419 arm is equal to the corresponding time to loss of asthma control in the placebo arm. The alternative hypothesis (H_1) is that the time to loss of asthma control in the active arm (AZD1419) is longer than in the placebo arm.

Time to loss of asthma control will be displayed graphically using a Kaplan-Meier plot (time axis, will be time from randomisation).

A Cox proportional hazard model will be fitted to the data to compare the treatments using the SAS[®] procedure PROC PHREG. Results of the analysis will be summarized as hazard ratio, 2-sided 95% confidence interval and p-value comparing AZD1419 with placebo. The hypothesis test will be 1-sided, with $\alpha=0.05$. The covariates for inclusion in the statistical model are described in Section 4.2.1.

For patients who withdraw from the study without reporting loss of asthma control, time will be censored at the date of withdrawal, if known, else at the patient's last clinical visit plus one day.

The assumptions underlying the statistical model will be explored. If the proportional hazards assumption does not hold then alternative methods will be explored which may include the following: 1) Extend the model to include exposure-time interaction term or 2) if the variable for which there is evidence of non-proportional hazards is a confounder, rather than the main exposure of interest then regression may be stratified.

Sensitivity analysis will be performed on the primary variable, see Section 5.1.

4.2.4.1 Loss of asthma control as group proportions

The proportion of patients with loss of asthma control will be compared between the two treatment groups at each clinical visit, using a generalized linear model based on a generalized estimating equations (GEE) approach, with occurrence of any loss of control as a binary outcome variable. Treatment group and visit will be included as factors in the model. The covariates for inclusion in the statistical model are described in Section 4.2.1. If a patient had

a ‘loss of asthma control’ event at one visit, the subsequent visits information should be removed. Each patient can only be counted once towards ‘loss of asthma control’.

This analysis will be carried out using a log-binomial regression model using PROC GLIMMIX in SAS with a random subject effect. The estimated treatment effect (i.e. the rate ratio of AZD1419 versus placebo), corresponding 95% confidence interval (CI), and two-sided p-value for the rate ratio will be presented.

In the case that If the GEE model fails to converge, due to the estimation method not being Restricted Maximum Likelihood (REML), then only the Mixed Model will be explored. The variance-covariance will be assumed to be unstructured. other options will be explored e.g. using the PROC GLIMMIX procedure in SAS. For PROC GLIMMIX, initially this will be fitted with a random statement fitting a random intercept and a Laplace approximation for maximum likelihood estimation. Again, to facilitate convergence, one or more of the covariates could be removed leaving the basic model. In case this model also fails to converge, the random statement will be removed which will result in a conventional logistic regression model being fitted.

The assumptions underlying the statistical model will be explored. If assumptions do not hold, then alternative strategies will be considered.

Summary statistics will also be presented for each treatment group at each visit.

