3.3.1 Proportion of patients who experience loss of asthma control

The proportion of patients who experience loss of asthma control during the 52-weeks of treatment will be a supportive measurement to the primary objective. The outcome variable will categorize each patient as having loss of asthma control symptom being met or not (yes=1/no=0).

The proportion of such patients will be calculated for each treatment group as:

Number of patients with loss of asthma control indication during the 52-week treatment period/ number of patients in treatment group

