4.2 Analysis methods

4.2.1 Patient disposition, demography data and patients characteristics

Patient disposition will be summarized using the All Patient analysis set.

The number of enrolled patients will be summarized. The number and percentage of patients within each treatment group will be presented by the following categories; randomised, not randomised (and reason), received study treatment, did not receive study treatment (and reason), completed treatment, discontinued treatment (and reason), completed study, and discontinued study (including reason).

The number and percentage of patients, who discontinued IP, but remained in the study will be presented by treatment group. Kaplan-Meier plots will be produced summarizing the time (in days) to discontinuation of IP and withdrawal from the study.

Demographic data such as age, gender, race and ethnicity will be summarized by treatment group for the FAS.

Various baseline characteristics will also be summarized by treatment for the FAS. These include weight, height, body mass index (BMI), medical, surgical and respiratory disease histories, history of allergic rhinitis, FEV₁ (pre and post-BD) at baseline, age at onset of asthma, asthma duration, the number of asthma exacerbations in the previous 12 months, the number of asthma exacerbations requiring hospitalizations in the previous 12 months, number of exacerbations resulting in antibiotic treatment, type of recent exacerbations, the number of admissions to ICU (Intensive Care Unit) for asthma during the hospitalization, eosinophil count, smoking status, nicotine consumption, reversibility test.

The following covariates are deemed to be of interest for inclusion in the statistical models of the primary and secondary endpoints. Possible covariates include but are not limited to: age at first asthma allergy status, whether hospitalized within the last year, race, sex, baseline spirometry variable measurements, baseline PEF, baseline ACQ-5 and baseline asthma symptom scores. For Blinded Deliverable review analyses, the following five covariates have been selected: age, race, sex, age at first asthma allergy status and whether hospitalized within the last year. For the final analysis, only age and gender will be included as covariates in the statistical models.

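### The only modelled comparison for the 52-week proportion losing asthma control (SAP 4.2.4.1) estimates a per-visit, hazard-type ratio, not the ratio of the proportions defined in SAP 3.3.1

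*SAP*

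**What the plan says.** SAP 3.3.1 defines the endpoint, separately for each arm, by this fraction: "Number of patients with loss of asthma control indication during the 52-week treatment period/ number of patients in treatment group". The same section ranks it below the primary endpoint: it "will be a supportive measurement to the primary objective".

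SAP 4.2.4.1 gives the model. The arms are to be compared at each clinical visit with a binary outcome. "Treatment group and visit will be included as factors in the model"; no treatment-by-visit term is listed. If a patient has a loss-of-control "event at one visit, the subsequent visits information should be removed". The first-named fit is explicit: "This analysis will be carried out using a log-binomial regression model using PROC GLIMMIX in SAS with a random subject effect". The output is a rate ratio of AZD1419 to placebo with a 95% CI and a two-sided p-value. SAP 4.2.1 adds the covariates: "For the final analysis, only age and gender will be included as covariates in the statistical models". If convergence fails, covariates may be dropped, and the last step is a conventional logistic regression.

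Three other places matter:
- SAP 4.2.5.7 (CompEx) specifies a log-binomial model with treatment as a factor and names its output a ratio of proportions.
- Protocol 8.5.4.1 plans longitudinal GEE modelling of the proportion at each visit, with no rule for removing records.
- SAP Section 6 does not list the removal rule as a change from protocol.

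**The concern.** Once the visits after the event are dropped, each remaining record asks whether a patient who was still in control has now lost it. That is a discrete-time hazard. The 3.3.1 endpoint is a cumulative risk over 52 weeks. When the event is common, as planned here, the two ratios can differ a good deal.

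The plan therefore contains no ratio, CI or p-value for the endpoint as 3.3.1 defines it. The output headed as group proportions would largely repeat the hazard ratio from the primary analysis. A reader could see 80% and 40% lost beside a ratio of about 0.34. A harmful effect would be inflated in the same way. The logistic fallback would change the measure again, so convergence would decide which quantity is reported.

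**Working it through.** **Inputs.** Controlled at Week 52: 20% placebo, 60% active (SAP 1.3), so 80% and 40% lost. Post-baseline visits: Weeks 1 to 13, 16, 20, 28, 36, 48 and 52 (SAP Table 6), 19 in all. Randomised: 81 (SAP 1.3), taken as 41 and 40.

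**The plan's own figure.** Hazard ratio = ln 0.6 / ln 0.2 = 0.511 / 1.609 = 0.317. Events for 90% power at two-sided 0.05 = 4 × (1.960 + 1.282)² / (ln 0.317)² ≈ 31.9, so 32. This reproduces the stated 32 events.

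**Target.** Ratio of the 3.3.1 proportions = 0.40 / 0.80 = 0.50.

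**What one visit contributes.** Take constant hazards from randomisation. The chance of losing control in an interval of d weeks, given control at its start, is 1 − S^(d/52), where S is the proportion controlled at Week 52.

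| Interval | Placebo (S = 0.2) | Active (S = 0.6) | Ratio |
|---|---|---|---|
| 1 week | 0.0305 | 0.0098 | 0.321 |
| 8 weeks | 0.219 | 0.0756 | 0.345 |
| 12 weeks | 0.310 | 0.111 | 0.358 |

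Every interval gives a ratio near the hazard ratio; none gives 0.50.

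**Pooled fit.** Expected-value fit to the at-risk records, with treatment and visit factors and no random effect or covariates:

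| Losses start at | Log-binomial ratio | Logistic fallback (odds ratio) |
|---|---|---|
| Week 0 | 0.337 | 0.300 |
| Week 6 | 0.342 | 0.295 |
| Week 9 | 0.346 | 0.291 |

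Harm: with 80% active and 60% placebo lost, starting at Week 6, the pooled ratio is 1.68; the ratio of proportions is 0.80 / 0.60 = 1.33.

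**Hazard shape.** Let active follow placebo until 40% are lost and then stay flat, with Weibull losses from Week 6. Shapes 0.4 to 2 give 0.43 to 0.48. Shape 0.3, strongly front-loaded, gives 0.53.

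**Random intercept.** The documents give no between-patient variance. Large-sample fits by quadrature, not SAS Laplace, were made with 80% and 40% lost held fixed and constant hazards from Week 0, 6 or 9:

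| Assumed SD of log-hazard | Ratio |
|---|---|
| 0 | 0.32–0.33 |
| 0.5 | 0.28–0.29 |
| 1 | 0.20–0.21 |
| 1.5 | 0.15 |

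The variance is weakly identified with one event per patient: in simulated trials of 70 patients with a random intercept and covariates, its estimated SD was near zero in 39% to 64%.

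**Would deleting the removal rule suffice?** No. If events are carried forward but one common effect is fitted across visits, the ratio is 0.42 to 0.44 under proportional hazards and 0.63 to 0.69 in the plateau patterns.

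**One record per patient.** The expected ratio is 0.50 without drop-out and 0.49 to 0.50 with equal drop-out of 10% to 15%. The delta-method standard error of the log ratio is √(0.6/(0.4 × 41) + 0.2/(0.8 × 40)) = 0.207, so the 95% CI at 0.50 is 0.33 to 0.75.

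**The case against.** - **The SAP never calls this output a ratio of proportions.** It says rate ratio, and its amendment history shows that wording about occurrence since the start of treatment was taken out of 4.2.4.1, so the choice may be deliberate. This stands in part: correct labelling would cure much of the problem. It would still leave the 3.3.1 endpoint without a modelled comparison.
- **A single common ratio is inferred.** The text says the arms are compared at each visit and gives no equation. This stands as an ambiguity. Visit-wise contrasts would not help, because after record removal each is conditional on still being in control. Nor can counting each patient once mean one record per patient, given a visit factor and a random subject effect.
- **Removal largely follows the design**, since patients leave 4 weeks after losing control (Protocol 4.3). True, and a reason to change the model rather than only the rule.
- **The proposed model also departs from Protocol 8.5.4.1 and has weaknesses.** Both stand, and the fix deals with them.
- **The consequence is limited.** The endpoint is supportive, and the crude proportions, by-visit summaries and Kaplan-Meier plot remain planned. This stands.

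A reader might infer that the SAP will report one particular ratio well below 0.34, such as 0.26. Simulations under assumed inputs can give that value, but the documents supply neither the between-patient variance nor the age and gender effects, so no single figure follows from them.

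**Conclusion.** The mismatch is real and should be corrected. The modelled result in 4.2.4.1 is a discrete-time, hazard-type ratio, and the endpoint in 3.3.1 is a 52-week proportion. At the planning values and under proportional hazards, the marginal fit gives about 0.34 where the ratio of proportions is 0.50; the logistic fallback gives an odds ratio of about 0.29 to 0.30. With the random effect, the value is roughly 0.15 to 0.33 under assumed variances.

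Three stronger readings are not supported. The model does not always exaggerate the effect, because the gap narrows in plateau patterns and reversed in one strongly front-loaded pattern. The proportions do not go unreported, because the crude figures are planned. The primary log-rank test and its type I error are not touched.

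**What to change.** In SAP 4.2.4.1, replace the visit-level model with text such as:

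> The 52-week proportion defined in Section 3.3.1 will be compared between arms by a log-binomial model with one record per patient and terms for treatment, age and gender. The ratio of proportions, 95% CI and two-sided p-value will be reported. If the model does not converge, Poisson regression with robust standard errors will be used. Kaplan-Meier Week-52 proportions, their difference and its 95% CI will be shown alongside.

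List this in SAP Section 6 as a change from Protocol 8.5.4.1, and keep the by-visit counts as description. If the per-visit model is kept, label it a discrete-time hazard ratio, list the removal rule in Section 6, and do not present it as the comparison of group proportions. SAP 4.2.4.9 borrows this method for an outcome counted since the start of treatment; there, only reconcile that wording with the removal rule.

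The cost is SAP wording and simple programming. The relative effect will probably look smaller. The log-binomial fit reached the probability boundary in 39% and 70% of simulated trials (300 per setting, without and with assumed age and gender effects), which is why a fallback that keeps the same measure is needed. The one-record model counts withdrawals as non-events: its ratio moves to 0.54 with drop-out of 5% active and 20% placebo, and to 0.46 with the reverse. The Kaplan-Meier figures are therefore needed beside it.

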4.2.4.2 Analysis of ACQ-5

Weekly average ACQ-5 score will be summarized by absolute score at each week by treatment group, together with the corresponding changes from baseline. Summaries will be descriptive statistics including N, mean, SD, median and range.

Weekly average ACQ-5 will be analysed longitudinally, using a mixed effects model for repeated measures (MMRM). Fixed categorical effects of treatment group and week will be included in the model with patient as a random effect. The baseline covariate will be the unweighted mean of the 5 questions at Visit 2 (Week 0). Further covariates for inclusion in the statistical model are described in [Section 4.2.1](#). At each week, all observed values will be used in this analysis. The variance-covariance matrix will be assumed to be unstructured. If the procedure does not converge then a compound symmetric variance-covariance matrix will be used instead. The model is:

*Weekly average in $ACQ_{ijk} = Treatment\ group_i + baseline\ ACQ_k + week_j + treatment_i * week_j + random\ patient\ effect_k + covariates_k;$ (where $i=treatment\ group, j=week$ and $k=patient$).*

Results will be presented for each timepoint and overall in terms of LSMEANS, treatment differences in LSMEANS, 95% confidence intervals and p-values.

The assumptions underlying the statistical model will be explored. If assumptions do not hold, then alternative strategies will be considered including transformation of the response variable or analysing the data using a non-parametric method.

4.2.4.3 Asthma daily diary score

Weekly average Asthma daily diary score will be analysed using the same method, MMRM as described in [Section 4.2.4.2](#).

Weekly average in Asthma daily diary $y_{ijk} = \text{Treatment group}_i + \text{baseline asthma daily diary score}_k + \text{week}_j + \text{treatment}_i * \text{week}_j + \text{random patient effect}_k + \text{covariates}_k$; (where i =treatment group, j =week and k =patient).

Results will be presented for each timepoint and overall in terms of LSMEANS, treatment differences in LSMEANS, 95% CI and p-values.

The assumptions underlying the statistical model will be explored. If assumptions do not hold, then alternative strategies will be considered as described in [Section 4.2.4.2](#).

Summary statistics for Asthma Daily Diary will be produced by treatment group over time for the weekly average and the change from baseline in weekly average. Daytime and night-time scores will be similarly summarized as well as total.

4.2.4.4 Reliever Bronchodilator (Use of SABA)

Responder variable Reliever Bronchodilator (yes/no) will be analysed using a logistic regression model with responder at Week 52 as the response variable and covariates of treatment and week. Further covariates for inclusion in the statistical model are described in [Section 4.2.4.2](#). The results of the analyses will be presented as odds ratios with associated 95% CI and 2-sided p-value.

The assumptions underlying the statistical model will be explored. If assumptions do not hold, then alternative strategies will be considered.

Summary statistics will be produced for the Reliever medication for each treatment group over time for the weekly average and the change from baseline in weekly average. A sensitivity summary table is also described for this variable in [Section 5.1](#).

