The investigational product, AZD1419 or matching placebo, will be administered once weekly using the commercially available and CE marked I-neb[®] Adaptive Aerosol Delivery [ADD] System from Philips Respironics.

AZD1419/placebo is supplied as a solution at a concentration of 2 mg/mL, 8 mg/mL and 16 mg/mL in phosphate-buffered saline.

Three inhaled dose levels of AZD1419/placebo, 1 mg, 4 mg and 8 mg may be investigated in a 12 week regimen consisting of 4 once weekly inhaled doses of 4 mg followed by 8 weeks of

inhaled doses of 1 mg, 4 mg, or 8 mg. The maximum possible dose that any patient will receive during the study is 8 mg.

The placebo for this trial is phosphate-buffered saline, pH 7.2.

Statistical methods and sample size

The primary efficacy variable is the time to loss of asthma control, and the primary analysis is to compare the time to loss of asthma control for AZD1419 with placebo. The time to loss of control in the AZD1419 group will be compared to that of the placebo group using a log rank test (with accompanying Kaplan-Meier plot). The hypothesis test will be one-sided, with $\alpha=0.05$.

The secondary outcome variables listed above will be analysed longitudinally using all measurements taken over the course of the study. Continuous variables will be modelled using mixed effects models; categorical outcomes will be modelled using generalized estimating equations. Additionally, all outcomes will be summarized by treatment group at each measurement time point.

This trial has about 90% power to yield a statistically significant ($\alpha = 0.05$, 2-sided) difference between the pooled active and placebo groups in time to loss of asthma control given that the cumulative number of controlled subjects at week 52 is 20% and 60% for control versus active respectively. Assuming a drop-out of about 10-15%, this will require about 70 patients in total (32 events).

TABLE OF CONTENTS

PAGE

TITLE PAGE.....	1
VERSION HISTORY	2
PROTOCOL SYNOPSIS	3
TABLE OF CONTENTS	7
1. INTRODUCTION	15
1.1 Background and rationale for conducting this study	15
1.2 Rationale for study design, doses and control groups.....	16
1.3 Benefit/risk and ethical assessment.....	17
1.4 Study Design	19
2. STUDY OBJECTIVES.....	21
2.1 Primary objective	21
2.1.1 Definition of Loss of asthma control	21
2.2 Secondary objectives	21
2.3 Safety objectives	22
2.4 Exploratory objectives	22

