1.4 Study Design

[figure not shown]
This phase 2a study is a randomized, double-blind, placebo-controlled trial designed to assess the efficacy and safety of 13 once weekly doses of inhaled AZD1419 administered to patients with eosinophilic asthma controlled on a maintenance treatment of ICS plus a LABA but no other controller medication.

A withdrawal design will be used where the first 6 doses of IMP will be administered as add-on to the patient's regular ICS + LABA medication. The controller medication will then be tapered down and discontinued during the next 3 doses of IMP, and the last 4 doses will be administered during a period of complete ICS and LABA withdrawal (see [Figure 1](#)). In addition the study drug dose level will be adjusted using an adaptive dosing scheme (defined in [Section 4.2.2](#)) based on appearance of flu-like symptoms. The primary endpoint is loss of asthma control, defined in [Section 2.1.1](#). When a patient meets the primary endpoint the patient will resume ICS + LABA and will be followed for an additional 4 weeks before discontinuing the study.

The total duration of patient participation will be up to 56 weeks. This includes a screening period of approximately 2-4 weeks, a 12 week dosing period and an up to 40-week observation period following the last dose, further outlined in [Section 4](#). The schedule of trial procedures is presented in [Table 1](#).

The study will start with a sentinel dosing period to be conducted at 1 or 2 selected study centers, during which 4 patients will be randomly assigned 1:1 either to placebo or AZD1419 at 4 mg, dosed once weekly. Sentinel patients will be observed at the clinic for 24 hours after each of the first two doses, for details see [Section 4.2.1](#). A Data Safety Monitoring Board (DSMB) will review safety data from these patients and approve enrollment of additional patients in the study (details in [Section 6.8.1](#)).

Figure 1 Phase 2a Study Design

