8.1 Statistical considerations

The primary outcome measure is loss of asthma control, as defined in Section 2.1.1. A number of secondary outcomes will also be considered (detailed below).

For the primary analysis of time to loss of asthma control, loss of control is considered to be permanent, given that patients are withdrawn from the study in such an event. Patients who withdraw from treatment and/or the study will have time to event censored at the first missed visit.

The primary hypothesis will be tested one-sided, with $\alpha=0.05$. All other hypothesis tests will be two-sided, with $\alpha=0.05$. Confidence intervals will be two-sided, at the 95% level

There will be no adjustments for multiplicity.

All efficacy analyses will be based on the Full Analysis Set, but with no imputation of missing values. For the summary statistics and analyses of secondary parameters, all data available at each time point will be used.

Safety analyses will include all patients who receive at least one dose of IMP (safety population) and all safety parameters will be described using the Safety population, using summary statistics presented by treatment group

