8.2 Sample size estimate

This trial has about 90% power to yield a statistically significant ($\alpha = 0.05$, 2-sided) difference between the pooled active and placebo groups in time to loss of asthma control given that the cumulative number of controlled subjects at week 52 is 20% and 60% for control versus active respectively. Assuming a drop-out of about 10-15%, this will require about 70 patients in total (32 events).

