8.5.5.8 Reliever medication

Reliever medication is recorded as taken using the ePRO device.

Summary statistics will be presented for each treatment group, grouped by study visit.

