Appendix F Asthma Daily Diary

Asthma Diary as used in AZ studies (from NIMBUS, slight variations exists, eg asking about reliever instead of rescue medication)

Endpoint/Variable	Item/question	Response
Morning diary		
Asthma symptoms	Please describe your asthma symptoms during the night	0 = no asthma symptoms 1 = you are aware of your asthma symptoms but you can easily tolerate the symptoms 2 = your asthma is causing you enough discomfort to cause problems with normal activities (or with sleep) 3 = you are unable to do your normal activities (or to sleep) because of your asthma
Night-time awakenings	Did your asthma cause you to wake up last night?	Yes No
Rescue medication	Since bedtime, did you use rescue medication during the night to relieve your asthma symptoms?	Yes No
(if “yes”)	Since bedtime, how many puffs of rescue medication did you take to relieve your asthma symptoms?	
Lung function	PEF/FEV ₁	
Evening diary		

Asthma symptoms	Please describe your asthma symptoms since this morning	0 = no asthma symptoms 1 = you are aware of your asthma symptoms but you can easily tolerate the symptoms 2 = your asthma is causing you enough discomfort to cause problems with normal activities (or with sleep) 3 = you are unable to do your normal activities (or to sleep) because of your asthma
Rescue medication	Since this morning, did you use rescue medication during the day to relieve your asthma symptoms?	Yes No
(if “yes”)	Since morning, how many puffs of rescue medication did you take to relieve your asthma symptoms?	
Lung function	PEF/FEV ₁	

Document Name: d2500c00003-csp-v1		
Document Title:	D2500C00003 Clinical Study Protocol version 1	
Document ID:	Doc ID-003111258	
Version Label:	3.0 Approved CURRENT LATEST	
Server Date (dd-MMM-yyyy HH:mm 'GMT'Z)	SignedBy	Meaning of Signature
17-Oct-2016 12:55 GMT+0100	██████████	██████████
18-Oct-2016 08:34 GMT+0100	██████████	██████████

Notes: (1) Document details as stored in ANGEL, an AstraZeneca document management system.

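### SAP 4.2.4.4 plans a test of a reliever responder at Week 52 without fully defining it, and the model is unsound whether it uses only Week 52 or all weekly records

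*SAP*

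**What the plan says.** SAP 4.2.4.4 states that a yes/no reliever responder variable is "analysed using a logistic regression model with responder at Week 52 as the response variable and covariates of treatment and week". The output is an odds ratio with a 95% confidence interval and a two-sided p-value. The same section also plans weekly summary statistics. SAP 3.3.6 derives only puffs per day and a weekly mean. SAP section 6 declares the logistic regression as an addition but does not define its response.

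The protocol gives two other plans. Section 8.5.5.8 says of reliever use: "Summary statistics will be presented for each treatment group, grouped by study visit". The synopsis says: "The secondary outcome variables listed above will be analysed longitudinally using all measurements taken over the course of the study", with generalized estimating equations for categorical outcomes.

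On missing data, protocol 8.1 says "All efficacy analyses will be based on the Full Analysis Set, but with no imputation of missing values" and "For the summary statistics and analyses of secondary parameters, all data available at each time point will be used". SAP 3.1.5 refers to sections 3.2 and 3.3 for endpoint rules, and 3.3.6 has none for a responder. SAP 5.1 adds zero and last-observation-carried-forward imputation for reliever use, for summary tables only.

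On follow-up, once a patient loses control "the patient will resume ICS + LABA and will be followed for an additional 4 weeks before discontinuing the study" (protocol 1.4). A sustained rise in SABA use is itself criterion (c) for loss of control (protocol 2.1.1, SAP 3.2).

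**The concern.** The section attaches a p-value to a response that two programmers could code differently, even in opposite directions. The model sentence also combines two designs: a single-time response, and a covariate that varies only if several weeks are analysed.

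On the single-week reading, the patients with Week 52 diaries are almost entirely those who did not have the primary event. If treatment changes who stays, the two groups of stayers are no longer comparable by randomisation, and the odds ratio cannot be read as a treatment effect on reliever use. On the weekly-row reading, repeated records from one patient would be treated as independent. Either way a reader of the study report could be misled by a secondary p-value. If the responder is settled only after unblinding, its definition becomes a data-dependent choice.

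**Working it through.** **Planning figures reproduced.** Protocol 8.2 assumes that "the cumulative number of controlled subjects at week 52 is 20% and 60% for control versus active respectively". Hazard ratio = ln 0.6 / ln 0.2 = 0.317. Schoenfeld events at 90% power, two-sided 0.05: 4(1.960 + 1.282)² / (ln 0.317)² = 32, as stated. Comparing 80% with 40% loss as proportions needs 30 per arm, so 60; 60/0.90 to 60/0.85 = 67 to 71, consistent with about 70 patients.

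**Patients with a Week 52 record, single-week reading.** SAP 1.3 gives 81 randomised; protocol 3.5 gives 1:1 allocation, so 40.5 per arm on average.

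| | Placebo | AZD1419 |
|---|---|---|
| In control at Week 52 | 40.5 × 0.2 = 8.1 | 40.5 × 0.6 = 24.3 |
| After 10–15% drop-out | 7.3–6.9 | 21.9–20.7 |
| Lost control in Weeks 48–52, still followed (constant hazard) | 40.5(0.2^(48/52) − 0.2) = 1.07 | 40.5(0.6^(48/52) − 0.6) = 0.97 |

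This gives about 7–9 against 21–25. The late losers would already be back on ICS + LABA. Without a Week 52 record: from 81 − 32.4 − 2.0 = 46.6 (no drop-out, late losers counted) to 81 − 0.85 × 32.4 = 53.5 (15% drop-out, late losers not counted), more than half of the 81.

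**Precision of that comparison.** With 8 against 24 patients and 50% use in each group, the 95% confidence interval factor is exp(1.96 √[1/(8 × 0.25) + 1/(24 × 0.25)]) = 4.95 each way.

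**Possible bias.** The following are assumptions, not in the documents: a standard normal severity score with logistic slopes of 0.5 to 2.0 per SD on both loss of control and reliever use; 50% use on placebo; and, as the true value, the odds ratio if everyone were observed at Week 52 off controller. Intercepts are set to the stated loss rates and results integrated over severity. Odds ratios are for use, AZD1419 against placebo, so below 1 favours AZD1419.

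- Loss 80%/40%, no effect on use, equal slopes 0.5, 1.0, 1.5, 2.0: observed 1.10, 1.36, 1.77, 2.35.
- Loss 80%/40%, conditional odds ratio 0.5 (true marginal 0.52 to 0.66): the observed value reaches 1 or more in 5 of 16 slope pairs, namely both slopes at least 1.5, or loss 1.0 with use 2.0. Elsewhere the benefit is diluted, for example 0.52 to 0.57 with both slopes 0.5.
- Loss 80%/80%: a null effect stays at 1.00; a true 0.66 becomes 0.59 with both slopes 2.0, a shift in favour of AZD1419.

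**Weekly-row reading.** Week is then a usable covariate, and patients contribute until they leave, so the counts above do not apply. But SAP 4.2.4.4 states no random patient effect and no working correlation, whereas the neighbouring models in 4.2.4.2, 4.2.4.3 and 4.2.4.5 to 4.2.4.7 include a patient effect.

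**Composite over the whole full analysis set.** Count loss of control or withdrawal as non-response, and let a share r of in-control completers respond, the same in both arms. With drop-out d, the response rates are 0.2(1 − d)r and 0.6(1 − d)r. Here the odds ratio is for response, so above 1 favours AZD1419.

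- d = 0.15, r = 0.5: 8.5% and 25.5%, odds ratio (0.255/0.745)/(0.085/0.915) = 3.68.
- d = 0.10, r = 1: 18% and 54%, odds ratio (0.54/0.46)/(0.18/0.82) = 5.35.
- The 95% confidence interval factors with 40 and 41 patients are 3.7 and 2.8.

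So the composite shows an odds ratio of about 3.7 to 5.35 even when reliever use among controlled patients is identical.

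**The case against.** The responder is not wholly undefined. The section heading, the yes/no label and the coded diary item on rescue use (ASMDMQ2, SAP 3.1.1 and 3.1.5) point to any SABA use, and protocol Appendix F asks exactly that: "Since bedtime, did you use rescue medication during the night to relieve your asthma symptoms". This stands. The gap is narrower: direction, days and aggregation.

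The single-week sample is one reading and not a fact. The week covariate and the synopsis point towards weekly rows. This also stands, so the 7–9 against 21–25 must be stated as conditional on that reading and on the planning rates. It does not rescue the model, because the weekly-row reading has its own defect.

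The observed-case step is an inference. The current SAP 3.1.5 does not repeat the protocol's no-imputation rule. But SAP section 6 lists no departure from it, and the SAP 5.1 imputations cover summary tables only, with carrying forward stopped at withdrawal.

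A reader might infer a breach of the intention-to-treat commitment in SAP 2.1. The documents do not support that: the full analysis set defines membership and does not promise a Week 52 observation for everyone. Thinning after loss of control follows from the design and affects every late secondary measure.

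Finally, this is one declared secondary analysis in a phase 2a trial without multiplicity control. That limits the stakes but does not make the p-value interpretable.

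**Conclusion.** The point holds. As written, SAP 4.2.4.4 cannot give an interpretable odds ratio or p-value on either reading. The missing definition and the conflict over week follow from the text alone. The expected counts rest on the planning rates, 81 randomised, drop-out unrelated to loss of control and the single-week reading.

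The direction and size of bias rest on assumed severity slopes. A reader might infer that the analysis will hide a real benefit of AZD1419. The documents do not support that: the bias runs against AZD1419 only if severity drives both loss of control and reliever use and AZD1419 delays loss of control. It is small under weak dependence (null odds ratio 1.10), and erases a benefit only under strong dependence. With equal loss in both arms there is none under the null, and a small shift the other way under a real effect. The primary log-rank test does not use this variable and is unaffected.

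**What to change.** Amend SAP 4.2.4.4 before unblinding, in one of two ways.

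(a) Drop the Week 52 test, or label it descriptive with no p-value, and keep the weekly summaries already planned there. This is closest to protocol 8.5.5.8.

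(b) If a test is kept: define the responder in the Week 52 window of SAP Appendix A Table 5 (direction, days, aggregation; the threshold is for the sponsor to choose); analyse all full-analysis-set patients with loss of control or withdrawal before Week 52 as non-response; state how an in-control patient without Week 52 diary data is classed; and remove week.

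Both need only SAP wording and programming, with no new data. Option (a) gives up a formal reliever comparison. Option (b) largely repeats the loss-of-control proportion in SAP 4.2.4.1, so the SAP should say that its result is not a reliever-only effect. Its interval width should not be compared directly with the observed-case factor, because the two analyses estimate different quantities.
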